15. BIBLIOGRAPHY							

EXPERIMENTAL SCHEMA

Figure 1: Standardized treatment protocol including study inclusion criteria and discharge checklist.

Discharge

Follow up within 30

days in clinic or via

phone or mail

PROTOCOL SIGNATURE

I confirm that I have read and understood this protocol, and I will conduct the study as outlined herein and according to the ethical principles stated in the latest version of the Declaration of Helsinki, the applicable ICH guidelines for good clinical practice, and the applicable laws and regulations of the federal government. I will promptly submit the protocol to the IRB for review and approval. Once the protocol has been approved by the IRB, I understand that any modifications made during the course of the study must first be approved by the IRB prior to implementation except when such modification is made to remove an immediate hazard to the subject.

I will provide copies of the protocol and all pertinent information to all individuals responsible to me who assist in the conduct of this study. I will discuss this material with them to ensure that they are fully informed regarding the study treatment, the conduct of the study, and the obligations of confidentiality.

Signature of Principal Investigator

Date

[name]

Principal Investigator Name (Print)

Johns Hopkins All Children's Hospital

Name of Institution

STUDY SUMMARY

Title	Antibiotic Instillation in Acute Complex Appendicitis for
	Prevention of Deep Space Surgical Site Infections
Short Title	Antibiotic Instillation in Appendicitis
IND	IND
Phase	Pilot Phase 2
Design	Randomized single blind control study
Study Duration	1 year
Study Center(s)	Single-center
Objectives	The primary objective is to evaluate the feasibility and safety of the use of antibiotic instillation in the treatment of complex acute appendicitis measured by enrollment rates and ability to complete all study tasks. Secondary objectives are to examine the rate of intra-abdominal abscess formation and post-operative length of stay following treatment of complex appendicitis in the setting of appendectomy with intra-operative suction alone compared to suction with intra-peritoneal antibiotic instillation
Number of Participants	A total of 36 patients will be randomized to two groups in this pilot study

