maximum 2g daily) and metronidazole (30mg/kg/day) therapy is used as pre-operative antibiotic treatment prior to pediatric appendectomy. [29] Intravenous ceftriaxone (50mg/kg/day, maximum 2g daily) and metronidazole(30mg/kg/day) is given post-operatively following the diagnosis of complicated appendicitis for a minimum of 48 hours following surgery. The maximum daily dosage of intravenous ceftriaxone administered during the conduct of the study will be 2g. We anticipate that the intra-peritoneal instillation of ceftriaxone will decrease the length of stay and decrease the post-operative development of deep organ space surgical site infection in patients with complicated appendicitis due to the longer contact with the inflamed area of the RLQ following removal of the nidus of infection, or the appendix. A small volume of instilled ceftriaxone (~10ml solution total) will be used so as not to instill a significant amount of additional fluid into the peritoneal cavity.

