4 STUDY DESIGN

This is a Prospective Randomized Open with Blinding of Endpoint (PROBE) pilot phase 2 study to evaluate the feasibility and safety of the use of antibiotic instillation in the treatment of complex acute appendicitis. All children equal to or greater than 20kg diagnosed with acute appendicitis and undergoing urgent appendectomy will be approached for enrollment for this study. As there is poor pre-operative diagnostic accuracy for simple versus complex appendicitis, all eligible patients presenting with acute appendicitis and their families will be approached for consent. Intra-operative assessment will diagnose complex appendicitis. Complex appendicitis will be defined as presence of any of the following: visible hole in the appendix, extra-luminal fecalith, diffuse fibropurulent exudate outside the right lower quadrant (RLQ)/pelvis, or intraperitoneal abscess. Patients will be excluded if they undergo non-operative management of appendicitis, do not undergo appendectomy at the time of operation, weigh less than 20kg, are pregnant, are unable to complete a 30day postoperative follow up, have impaired renal function (CrCl <15mL/min), have a history of neurological conditions (such as encephalopathy, seizures, myoclonus, and nonconvulsive status epilepticus), or are allergic to penicillin or cephalosporins that prohibit the use of the antibiotic intra-peritoneal instillation. Patients with a history of anaphylactic reactions to penicillin or cephalosporins will be excluded from this study. Patients with a penicillin allergy who have previously received IV cephalosporins without allergic reaction will be considered for inclusion in this study.

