Study participants will be randomized in a 1:1 ratio using permuted blocks of 4 and 6 using a computer-generated randomization scheme. The treatment category assignments will be placed in consecutive numbered envelopes concealed from study staff until randomization. In the operating room, once the patient is diagnosed with complicated appendicitis, then the next sequential envelope will be opened and the patient will be assigned to that treatment arm. The surgeon and team administering the treatment will not be blinded; however, patients, their families, and hospital caregivers outside of the operating room will be blinded to the treatment. Post-operative protocols will be the same for both groups and includes continuation of intravenous antibiotics (Study Schema, and Fig 1). Once complex appendicitis is diagnosed, and a successful appendectomy occurs, then the patient will be transitioned to intravenous ceftriaxone (50mg/kg/day, maximum 2g daily) and metronidazole (30mg/kg/day) post-operatively. Both study groups will receive a minimum additional 48 hours of intravenous ceftriaxone and metronidazole, as per our weight based current standard of care. Patient status and post-operative recovery back to baseline will dictate discharge or continued hospitalization. Pending their clinical course, patients will be either transitioned to broadspectrum oral antibiotics or continued on intravenous ceftriaxone and metronidazole until their discharge from the hospital. Our standardized discharge criteria includes: temperature less than 38.5°C for the previous 24 hours, improved abdominal pain without the use of narcotics, and tolerance of enteral intake. Once these criteria have been met, and at the surgeon's discretion, the patient will be discharged home with routine follow-up (either a clinic visit, telemedicine visit, or a phone call) within 30 days after surgery.

If the patient remains hospitalized on post-operative day 7 (plus or minus 1 day) related to postoperative care of complicated appendicitis, and does not meet discharge criteria as listed, then they will undergo subsequent imaging studies (abdominal ultrasound or CT abdomen-pelvis) to evaluate for intra-abdominal abscess or phlegmon. If patients are found to have an abscess or phlegmon, they will continue to receive ongoing antibiotic treatment with or without percutaneous aspiration and/or drainage at the discretion of the surgeon and interventional radiologist.

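### Length of stay ends at a discretionary discharge by a surgeon who may know the arm, so the PROBE design's blinded endpoint is not secured for this exploratory outcome

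*Combined protocol and SAP*

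**What the plan says.** Section 4 names the design: "This is a Prospective Randomized Open with Blinding of Endpoint (PROBE) pilot phase 2 study". The Study Summary calls it "Randomized single blind control study". On who is blinded, section 4 says: "The surgeon and team administering the treatment will not be blinded". Patients, families and hospital caregivers outside the operating room are to be blinded.

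Both arms share one post-operative protocol, at least 48 further hours of intravenous antibiotics, and one set of discharge criteria: "temperature less than 38.5°C for the previous 24 hours, improved abdominal pain without the use of narcotics, and tolerance of enteral intake". Section 4 says of the general course: "Patient status and post-operative recovery back to baseline will dictate discharge or continued hospitalization". The operative sentence on discharge is: "Once these criteria have been met, and at the surgeon's discretion, the patient will be discharged home with routine follow-up".

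Length of stay stands beside abscess rate in the Study Summary's secondary objectives and is listed in sections 1.1.2 B, 4 and 11.1. Section 2 states the expected direction: "We anticipate that the intra-peritoneal instillation of ceftriaxone will decrease the length of stay". Section 7.2.3 has the ceftriaxone amount entered in the electronic record and its dose and route documented in the operative note. Section 4 also sets up an independent clinical endpoint committee for complications and endpoints. Section 12 compares continuous outcomes by t-test or Mann-Whitney U and calls the secondary analyses exploratory and unpowered, but intends them to guide the design of a larger study.

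**The concern.** A PROBE design accepts open treatment because the endpoint is assessed by someone who does not know the arm. That works for events that can be adjudicated from records, such as an abscess. Length of stay is different: its value is fixed when a clinician decides to discharge, and nobody adjudicates it afterwards. If that clinician knows the arm and shares the protocol's expectation, the stay can differ between arms while recovery does not.

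At stake is the reading of one of the two efficacy outcomes named in the Study Summary. A shorter stay in Arm B could reflect faster recovery or earlier release once ready, and the plan describes no measure of readiness to tell these apart. The estimate is meant to inform a larger trial. More patients would reduce its random error but not a bias built into how the outcome ends.

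**Working it through.** The plan has no figure to reproduce here. The check is a reading of the relevant sections together, followed by an illustration on stated assumptions.

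**Step 1: what ends the stay.** Under section 4, discharge needs the three criteria and then the surgeon's discretion. The criteria set the earliest time and the surgeon sets the actual time.

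**Step 2: what that surgeon may know.** The operating surgeon knows the arm (section 4). The documents do not say that the discharging surgeon is the same person, nor do they require a blinded one. Another surgeon could read the arm in the operative note (section 7.2.3), and no section describes masking it.

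**Step 3: where bias can enter.** It cannot enter through discharge before the 48-hour minimum or before the temperature, narcotic and intake conditions are met, because these apply equally to both arms. Two routes remain: unequal delay after readiness, and unequal judgement of whether pain has improved, for which no threshold is given.

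**Step 4: safeguards.** The endpoint committee is described as independent. The text does not say that it is blinded or that it judges readiness for discharge, and it could not alter a past discharge date in any case. No readable section records when the criteria are first met. Figure 1 is captioned as including a discharge checklist, but its content is not available in the text reviewed, so it may already record some of this.

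**Step 5: illustration, not an estimate.** Inputs: 18 per arm (section 12). Assumed: identical recovery, a constant delay d after readiness in every patient of one arm only, a common standard deviation s, and two-sided alpha 0.05. The documents give no s, no d and no alpha.

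SE = s × √(2/18) = s/3. The expected arm difference is d, all of it bias. The chance of p < 0.05 is Φ(d/SE − 1.96) + Φ(−d/SE − 1.96). For s = 1 and d = 0.5, d/SE = 1.5, giving Φ(−0.46) + Φ(−3.46) ≈ 0.323.

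| s (days) | d = 0.25 day | d = 0.5 day | d = 1 day |
|---|---|---|---|
| 1 | 12% | 32% | 85% |
| 2 | 7% | 12% | 32% |
| 3 | 6% | 8% | 17% |

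A simulation with the Mann-Whitney U test gave 7–9%, 12–23% and 36–65% for the same three delays. It assumed a lognormal time to criteria with median 4 days, log-SD 0.3 or 0.5 and a floor at 2 days. The nominal rate is 5%. The range runs from negligible to serious and depends wholly on values that the documents do not supply.

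**The case against.** The strongest reply is that discretion is narrow and little turns on it. Both arms share the same antibiotic minimum and criteria, and section 4 says that patient status and recovery dictate discharge. An enthusiastic surgeon cannot send an Arm B child home early. This stands as a limit on the routes, but the discretion clause still follows the criteria and nothing bounds the delay after them.

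Second, the discharging surgeon might be blinded in practice, since caregivers outside the operating room are meant to be. A reader might infer that the operating surgeon always discharges; the documents do not say so. The supportable statement is that the surgeon may know the arm.

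Third, the plan is not without other evidence. Pain scores from blinded patients, pain medication use and readmission would help to interpret a shorter stay. They are partial evidence and do not give the time of readiness.

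Fourth, a reader might infer that length of stay is the outcome most open to expectation. That is not shown: drainage and some imaging are also discretionary.

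Fifth, the analysis is exploratory and imprecise. With 18 per arm, the 95% half-width for a mean difference is about 1.96 × s/3, or 0.65, 1.31 and 1.96 days for assumed s of 1, 2 and 3. A half-day bias would lie within that. This stands, and it is why the point is an improvement to the pilot rather than a flaw in its main conclusion.

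Finally, a readiness measure is not free of the same problem. The documents do not say that those ordering narcotics or advancing diet are blinded.

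**Conclusion.** The concern holds in a limited form. The blinded-endpoint property is not secured for length of stay, because the outcome ends at a discretionary decision by a surgeon who may know the arm, in a protocol that anticipates a shorter stay with instillation. This rests on the wording of sections 2, 4 and 7.2.3 and on no numerical assumption. It shows that bias is possible, not that it occurs.

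Its size cannot be derived from the documents. A reader might assume a mean stay of 4 to 6 days, subtract the 2 days of mandatory antibiotics, and call a half-day shift 12.5% (0.5/4) to 25% (0.5/2) of the discretionary stay. The documents do not support this. Discretion begins only once the criteria are met, so days with fever, narcotic use or poor intake are not discretionary, and neither the stay nor the interval from readiness to discharge is given. The table above is conditional on assumed values and should not be read as an estimate.

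The primary feasibility benchmarks for participation and completion are unaffected. The weight of the point lies in the length-of-stay signal carried into the larger trial.

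**What to change.** Keep actual length of stay. Add to the between-arm comparison the time from end of surgery to first meeting all three discharge criteria already in section 4. Derive it from charted temperature, narcotic administration, pain scores and enteral intake, or from time stamps on the existing discharge checklist. Where improved pain needs a judgement, have the existing endpoint committee make it without knowledge of the arm, and state that blinding in the protocol. Report the gap between readiness and actual discharge by arm. If stays differ but readiness does not, the gap will show it. Discharge practice itself does not change.

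The cost is modest. Vital signs and pain scores are already scheduled in section 9, and inpatient pain medication is tracked under section 4. Enteral intake and timed narcotic use are not in the study calendar, so a CRF field or two is needed, with a working definition of improved pain for abstraction and some chart work for 36 patients. The new measure reduces the bias but may not remove it. Demoting actual length of stay to a purely descriptive outcome would be a further step. It is a debatable trade-off and is not needed here.

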1.1.2 Secondary objectives

- A. To evaluate preliminary efficacy of antibiotic solution instillation following diagnosis of complex appendicitis.
- B. To compare the following outcomes between patients who receive or do not receive antibiotic solution instillation following diagnosis of complicated appendicitis: operative time, length of stay, post-operative antibiotic use, post-operative pain medication use, need for post-operative imaging, readmission rates, and the development of intra-peritoneal abscess requiring percutaneous aspiration and/or drainage within 30-days following appendectomy.

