Patients will undergo telephone, telemedicine visit, or in-person clinic follow-up within 30days of their discharge following their appendectomy. If patients present with symptoms at these checks or independently present to an emergency department, they will undergo routine evaluation and imaging as clinically indicated. Other parameters that will be tracked include development of superficial or deep surgical site infection, inpatient pain scores, inpatient pain medication use, and post-operative length of stay.

An independent clinical endpoint committee will be formed to evaluate for study related complications and endpoints. For consistency and future ease of a prospective multicenter trial, definitions of intraoperative findings of complicated appendicitis, postoperative percutaneous drainage or aspiration of intraperitoneal fluid collection, surgical site infection, postoperative sepsis, readmission and/or reoperation will be reported according to the National Surgical Quality Improvement Program Pediatric Operations Manual, January 2022 edition. [31]

We will evaluate patient retention and recruitment along with the process of instilling antibiotic solution into the intra-peritoneal space in this feasibility study. We will primarily focus on recruitment, enrollment, and retention rates in this pilot study. We will also evaluate patient outcomes associated with intra-peritoneal instillation of antibiotics to determine not only postoperative complication rates, but also length of stay, pain scores, pain medication use, superficial surgical site infections, and adverse events related to the antibiotic instillation. Patients and their families will be blinded to their randomized treatment groups, and will be followed for 30 days following appendectomy.

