4.3 Study Duration

We will begin screening patients after IRB approval of our pilot study. We will continue screening and inclusion in the trial until enrollment is met. We suspect this will take approximately eighteen months. The duration of participation will be approximately 30-days from the time of appendectomy. We will continue our pilot study until we have enrolled a total of 36 patients.

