5.2 Exclusion Criteria

- 5.2.1 Patient is pregnant
- 5.2.2 Patient has a penicillin or cephalosporin allergy that is severe or anaphylactic in nature, prohibiting the use of these antibiotics
- 5.2.3 Patient has simple appendicitis
- 5.2.4 Patient who undergoes appendectomy following failed or planned medical management of appendicitis
- 5.2.5 Patient has impaired renal function (CrCl <15mL/min)
- 5.2.6 Patient has history of neurological conditions such as encephalopathy, seizures, myoclonus and non-convulsive status epilepticus
- 5.2.7 Patient has a known inability to complete a 30day postoperative follow up

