9 STUDY CALENDAR

MONTHLY Calendar

Test / Procedure	Pre-	Surger	POD	POD	POD	POD	POD	POD	POD	POD
	study	У	1	3	4	5	0	/	14	<30
Informed consent	Х									
Medical history	Х									
Eligibility criteria	Х									
Vital signs ²	Х		Х	Х	Х	Х	Х	Х	Х	
Physical examination ²	X		Х	Х	Х	Х	Х	Х	Х	
CBC with diff ²	Х			X ³						
Urine pregnancy test ⁴	X									
Pain Score ²	Х	Х	Х	Х	Х	Х	Х	Х	Х	Х
Randomization and record of treatment group		Х								
Telephone or In- person Follow up									Х	Х
Pre-operative imaging (US or CT scan)	Х									
Post-operative imaging (US or CT Scan) ⁵								X ³		

1 All Pre-study/Screening procedures should be completed within 24 hours of study enrollment

2 To occur if the patient is still admitted, or seen in follow up

3 To occur at the discretion of the surgeon when clinically warranted

4 Required for any female greater than 10 years old prior to receiving general anesthesia

5 If patient continues to have an elevated WBC, pain on exam, a fever within the last 24 hours or is unable to tolerate a diet.

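### Outcomes and adverse events run to 30 days after surgery, but no contact or record check is required at or after day 30

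*Combined protocol and SAP*

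**What the plan says.** **The window.** Section 1.1.2 lists "development of intra-peritoneal abscess requiring percutaneous aspiration and/or drainage within 30-days following appendectomy" among the secondary outcomes. Section 8.1 collects adverse events for 30 days from the operative date. Section 4 says that patients and families "will be followed for 30 days following appendectomy", and Section 11.1 says the same. Section 4.3 states: "The duration of participation will be approximately 30-days from the time of appendectomy".

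**The contacts.** Section 4 first says "the patient will be discharged home with routine follow-up (either a clinic visit, telemedicine visit, or a phone call) within 30 days after surgery". Its later text on follow-up allows telephone, telemedicine or "in-person clinic follow-up within 30days of their discharge following their appendectomy", so the count there starts at discharge. The Experimental Schema reads "Follow up within 30" days and adds mail as a route. In the Section 9 calendar, the row "Telephone or In- person Follow up" is marked in the last two columns, POD 14 and POD <30. The calendar header is damaged in the text available to us, so whether the last column means before day 30 or up to day 30 cannot be settled.

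**The benchmark.** Section 12 (Analysis for Aim 1) requires at least 75% of those who agree to participate to complete every measurement time point.

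**The concern.** A limit of the form 'within 30 days' fixes the latest day for a contact and leaves the earliest day open. An outcome counted to day 30 needs the opposite: a last look on day 30 or later. Under the present text, a child whose contacts were all made early, and who is then drained or readmitted at another hospital, has met every contact rule. If nobody tells the study, the record shows no event.

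The results mainly exposed are the 30-day abscess and readmission rates and late adverse events. Section 12 says these exploratory results will guide the design of a larger study, and Section 2 names fewer abscesses as that study's aim. The primary feasibility aim is affected too: the last time point in the completion benchmark is not tied to the end of the window, so a participant can count as complete while status to POD 30 is unknown.

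**Working it through.** The plan gives no figure on this point to reproduce. The check sets the timing rules against the window and then works out the size.

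**1. Timing rules against the window (POD 0 to 30)**

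| Place | Latest day for a contact | Earliest day |
|---|---|---|
| Section 4, discharge text | POD 30 | none |
| Section 4, later follow-up text | 30 days after discharge | none |
| Experimental Schema | 30 days, anchor not stated | none |
| Section 9, first mark | POD 14 | POD 14 |
| Section 9, last column | POD <30 (or ≤30) | none |

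The two Section 4 limits are nested. For discharge on POD d, the second limit falls on POD 30 + d. Both arms receive at least 48 hours of postoperative intravenous antibiotics, so d is about 2 or more and the limit is about POD 32 or later. The two rules differ only for contacts after POD 30, which the second permits but does not require.

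**2. Other text that might close the window**

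- Section 8.1 promises review of adverse events through 30 days. It finds them by questioning at contacts, volunteered reports, examination and tests, and names no closing step.
- Section 4 provides evaluation for patients who go to an emergency department, but gives no route by which the study learns of care elsewhere.
- Section 13 uses medical records to verify data. It requires no search through POD 30.
- Section 7.5 (three calls and a certified letter) applies to participants who repeatedly miss visits and cannot be reached, not to those contacted early.
- The Section 5.2 exclusion, "Patient has a known inability to complete a 30day postoperative follow up", acts only at entry.
- The endpoint committee in Section 4 can judge only events that reach it.

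**3. Days with no later scheduled contact**

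Formula: 30 minus the day of the last contact, with the calendar followed (POD 14 plus one later contact). The second contact day is assumed, to span what the calendar allows.

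| Second contact | Days uncovered | Share of window |
|---|---|---|
| POD 15 | 30 − 15 = 15 | 15/30 = 50% |
| POD 21 | 30 − 21 = 9 | 9/30 = 30% |
| POD 28 | 30 − 28 = 2 | 2/30 = 7% |
| POD 30 | 30 − 30 = 0 | 0% |

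These are shares of days, not of events.

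**4. Weight of one missed event**

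Section 12 plans 18 per arm, so one event is 1/18 = 5.6 percentage points. Exact (Clopper-Pearson) 95% intervals:

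- 1/18 = 5.6%, interval 0.1% to 27.3%
- 0/18 = 0%, interval 0% to 18.5%

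Missing the only event in an arm would turn the first line into the second.

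**The case against.** The strongest reply is that the plan does commit to 30 days: Sections 4, 4.3, 8.1 and 11.1 all say so, and only the operational closing step is missing. Case report forms and the external operations manual cited for definitions might supply it, though neither can be seen. That shows intent, and sites may well call near day 30. It does not change what the protocol requires, and a POD 15 call satisfies it.

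The calendar header is damaged, and if the last column meant day 30 itself, much of the gap under the calendar would close. But the Section 4 discharge text shows the same gap without the calendar.

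The documents do not say that unassessed days are coded as event-free, and Section 12 says missing data will be characterised and not imputed. This is fair as far as it goes. However, a participant whose contacts were all early has no missed contact to flag, and no rule separates no event from not assessed through POD 30.

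The limits on weight stand. The efficacy outcomes are exploratory and unpowered, the two intervals above overlap heavily, and 1/18 is the weight of any missed event whatever its cause. Drug-related effects are little exposed: Section 8.1 expects them within 48 hours and Section 12 within 12 hours, when participants are still inpatients. In Section 1.1.2 the 30-day wording clearly governs abscess; for readmission the period rests on the general follow-up statements.

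Section 8.2 ends serious adverse event collection 48 hours after instillation. That is a separate inconsistency, which this change would not resolve.

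**Conclusion.** The concern holds. Outcomes and adverse events are counted to POD 30, while the contact rules, apart from POD 14, set only latest days with mixed anchors. Full compliance can leave 0 to 15 of the 30 days without a later contact, depending on an assumed contact day; 15 is the extreme. One missed event lowers an arm's rate by 5.6 points. How many events would be missed cannot be derived, because the documents give no onset pattern. The expected direction is rates that are too low; no difference between arms is shown. The conclusion rests on the protocol text alone and does not suppose that sites will in fact call early. It is a point the sponsor should correct, because the correction is cheap and these rates feed the next trial.

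**What to change.** 1. Count from the day of surgery in the Experimental Schema, both follow-up statements in Section 4, and the Section 9 calendar.
2. Retime the last calendar contact as a telephone or telemedicine study contact at or after POD 30 with a stated window, for example POD 30 to 37, identical in both arms. Keep the POD 14 contact and leave routine clinical follow-up as it is.
3. At that contact, ask about all care, imaging, drainage, readmission and adverse events through POD 30, including at other hospitals, and review the chart through POD 30. Count only events through POD 30.
4. Name this contact as the final time point for the 75% completion benchmark in Section 12, and extend the participation length in Section 4.3 to the end of the contact window.

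**Cost.** The change means a later call in place of an existing one, with added questions, and a chart check for 36 participants; there is no new clinical procedure. It needs an amendment approved by the IRB (Section 14.3). The interval after the POD 14 contact becomes 16 to 23 days (30 − 14 to 37 − 14), which puts more weight on recall and is one reason for the chart check. The pain score in the last calendar column would move with the contact unless it is timed separately. A few more contacts may fail and completion may come out slightly lower, but that is information on retention that a feasibility pilot should report.
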